Pharmacokinetic Profile	
 • Oral bioavailability: 40-65% • Plasma concentrations linear and time-independent • Dose proportional between 200 to 600 mg • T_{max}: 2 to 4h (tablet) • C_{max} delayed 1h by food • C_{max}: 3.7 to 4.8µg/mL (200 mg dose) • Terminal half-life: 15 h (range 10-15h) • Impact of ethnicity and gender • Protein binding: 60% [21] 	
 • Oral bioavailability: 95% • Plasma concentrations approximately dose dependent within therapeutic range but unclear when below • T_{max}: 1.5 to 3 h (tablet) • No food interaction • C_{max}: 200 to 1,000 ng/mL (100-300 mg) • Terminal half-life: 13 h (mean across single dose studies, range wide). • Protein binding: 40% [22,23]
Metabolism (human)	
 • Amide pathway (major) and oxidative pathway (minor) • Substrate: multiple CYP450 including CYP3A4/3A5 • Metabolised by liver • ≤5% intact drug excreted in urine [24] 
No anticipated interaction with Flecainide metabolism (different CYP450 pathway) 200 to 400 mg/day (in narcolepsy) Registration: 1992 (France), 2003 (USA)
	
 • Substrate: CYP2D6 (mainly) and 1A2 • Metabolised by liver • ~30% intact drug in urine [25] 
No anticipated interaction with Modafinil metabolism (different CYP450 pathway) 100 to 300 mg/day (in tachyarrhythmia) Registration: 1983 (France)

Adverse events cited in SmPC from EMA (chronic therapy, with above posology)		
>10%	
 • Headache 	
 • Dizziness, light headedness, headache • Visual disturbances • Depression, anxiety, insomnia
1-10%	
 • Nervousness, insomnia, anxiety, depression, confusion • Dizziness, somnolence, paraesthesia • Tachycardia, palpitation • Blurred vision • Abdominal pain, nausea, dry mouth, diarrhea, constipation and others • Chest pain, asthenia • Increased liver function tests 	
 • Paraesthesia, ataxia, tremor, syncope... • Palpitation • Nausea, vomiting, abdominal pain and others • Dyspnea • Asthenia, fatigue, oedema

An extensive list of adverse events is presented in each SmPC, albeit from patients on chronic treatment, frequently on concomitant therapy and at a much higher dose in case of flecainide. These documents will serve as a basis to identify Suspected Unexpected Serious Adverse Reactions (SUSAR) in this trial (also see Section 7.2.2).

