5.1.3. Timing of IMP doses and administration

IMP will be administered only to subjects included in this trial, following the procedures set out in the trial protocol.

IMP (2 capsules modafinil or placebo plus 2 capsules flecainide or placebo; 4 capsules in total) will be administered in the morning. IMP will be swallowed before meal with 150 mL tap water at 8:00 h (\pm 1 h).

For subjects aged above 65 years:

On the first, second and third day of each treatment period, 1 modafinil and 1 flecainide capsule will be taken. From the fourth to the last day of each treatment period, the regimen will be as described above.

The time of IMP intake will be recorded in the subject diary daily.

Dose adjustments will not be permitted.

In each treatment period, first IMP intake will take place on the day after IMP dispensation, i.e. on the day after visit VR, V1C or V2C, respectively.

In each treatment period, last IMP intake will take place on the day of visit V1B, V2B or V3B, respectively.

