##### Treatment periods

The periods from the day after visits VR, V1C, and V2C, to the dates of visits V1B, V2B, and V3B respectively, will be defined as the three treatment periods of this trial.

Data collected at visits V1B, V2B, and V3B will be considered as end-of-treatment values for their respective treatment periods.

If an early discontinuation visit (EDV) occurs after 7 or more IMP intakes, and not more than 3 days after the last IMP intake, the data collected at the EDV will be assigned to the end of the ongoing treatment period for statistical analyses.

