## 5.6 Efficacy Analysis

Efficacy will be assessed by evaluation of the following variables:

- Epworth Sleepiness Scale (ESS) score change from baseline at the end of each treatment period
- ESS score responder rate at the end of each treatment period
- Absence of residual somnolence at the end of each treatment period
- Psychomotor Vigilance Test (PVT) variable change from baseline at the end of each treatment period
- Montreal Cognitive Assessment (MoCA) score change from baseline at the end of each treatment period
- Actimetry change from baseline at the end of each treatment period
- Number and duration of diurnal involuntary sleep attacks (subject diaries) change from baseline at the end of each treatment period
- Episodes of somnolence (subject diaries) change from baseline at the end of each treatment period

The Full Analysis set as well as the Per Protocol set will be used for the analysis of efficacy data.

**Treatment periods** will be considered as evaluable for efficacy analysis only if the following rules are satisfied:

- IMP is taken for at least 7 days during the treatment period
- Last IMP intake is at most 3 days before the corresponding end-of-treatment visit, i.e. a maximum of 3 IMP intakes can be missed leading up to the end-of-treatment visit.

**Washout periods** will be considered as evaluable for efficacy analysis only if the preceding treatment period is evaluable and the last IMP intake is 6 or more days before the corresponding end-of-washout visit.

For the purposes of these rules, EDVs are considered as end-of-treatment (if the preceding scheduled visit was VR/V1C/V2C) or end-of-washout (if the preceding scheduled visit was V1B/V2B) visits.

A trial period not being evaluable for efficacy analysis according to these rules is considered a major protocol deviation.

Efficacy analyses for the FAS will be performed using data available from all scheduled visits, as well as EDV visits satisfying the above criteria. Efficacy analyses for the PP will be performed using only data from trial periods unaffected by major protocol deviations.

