### Evaluability of pharmacokinetic data

PK samples performed at the end of **treatment periods** will be analysed if an IMP intake was performed in the morning before the PK sample.

PK samples performed at the end of **washout periods** will be analysed if the last IMP intake is 6 or more days before the PK sample, and if the preceding end-of-treatment PK sample is evaluable according to the above rule.

Deviations from these rules will be considered as major protocol deviations in relation to PK analysis.

The following tables and listing will be presented:

Table 15.4.1.S Summary of Pharmacokinetics Concentrations – PK Analysis Set

Table 15.4.2.T Summary of Pharmacokinetics Concentrations – PK Analysis Set

The concentrations of modafinil and flecainide at each visit will be summarised using the geometric mean, geometric standard deviation, and geometric coefficient of variation in addition to the default summary statistics.

Listing 16.2.5.2 Pharmacokinetics Concentrations – Enrolled

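### The 3-day intake rule suits the ESS but allows PVT and MoCA tests done 24 to 72 h after the last dose to count as on treatment in the Per Protocol analysis

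*SAP*

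**What the plan says.** SAP 5.6 lists the efficacy variables together, from ESS to diary data, and gives them one evaluability rule with two conditions. The first is "IMP is taken for at least 7 days during the treatment period". The second is "Last IMP intake is at most 3 days before the corresponding end-of-treatment visit"; the SAP spells this out as up to three missed doses. A period that breaks the rule carries a major deviation, and "Efficacy analyses for the PP will be performed using only data from trial periods unaffected by major protocol deviations". SAP 4.6 applies the same 3-day limit to early discontinuation visits that follow 7 or more intakes, and their results then count as end-of-treatment results. SAP 5.6.5 (PVT) and 5.6.6 (MoCA) add no intake condition.

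Protocol 5.1.3 plans something tighter: "In each treatment period, last IMP intake will take place on the day of visit V1B, V2B or V3B, respectively", in the morning at 8:00 h ± 1 h. SAP 5.7 also holds PK to a tighter standard. An end-of-treatment sample "will be analysed if an IMP intake was performed in the morning before the PK sample", and a breach counts as major for the PK analysis only.

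SAP 3.1 says that ESS, PVT and cognition are repeated on the Per Protocol set to show robustness.

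**The concern.** The three main efficacy measures look at different time windows. The ESS asks about the past week (Protocol 6.4.1), so a subject who missed the last three doses still reports on about 7 - 3 = 4 treated days. PVT is the mean of that day's sessions (SAP 5.6.5), and MoCA is to be done in the morning (Protocol 6.4.3). Neither looks back.

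A rule built for a weekly recall can therefore label a largely untreated test as an active-treatment result. Under placebo a missed dose changes nothing pharmacologically; under either THN102 dose it removes the drug being tested. At stake is the supportive evidence on attention, vigilance and cognition, which are stated secondary objectives. The FAS analysis uses all scheduled visits, so the Per Protocol analysis is where such tests would be expected to drop out.

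**Working it through.** **Inputs.** Protocol Table 1 gives modafinil "Terminal half-life: 15 h (range 10-15h") and flecainide 13 h, described as a mean over single-dose studies with a wide range. Protocol 1.1 gives flecainide 12.2 h in the first phase I trial. Dosing is at 08:00 and default PVT sessions run from 10:00 to 16:00.

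**The plan's own figure first.** Protocol 1.3.1 says that steady state is reached after about 3 days. With first-order kinetics, the share of steady state reached at 72 h is 1 - 0.5^(72/15) = 96.4% for modafinil and 1 - 0.5^(72/13) = 97.8% for flecainide. The half-lives agree with that statement, and the same interval off drug removes the same share.

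**Drug left after the last dose**, 0.5^(t/half-life):

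| Hours since last dose | Intakes missed by the visit morning | Modafinil, 15 h | Modafinil, 10 h | Flecainide, 13 h | Flecainide, 12.2 h |
|---|---|---|---|---|---|
| 24 | 1 | 33.0% | 19.0% | 27.8% | 25.6% |
| 48 | 2 | 10.9% | 3.6% | 7.7% | 6.5% |
| 72 | 3 | 3.6% | 0.7% | 2.2% | 1.7% |

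At the limit, PVT at 10:00 to 16:00 falls 74 to 80 h after the dose. That leaves 3.3% to 2.5% of modafinil (15 h) and 1.9% to 1.4% of flecainide (13 h). With intake as planned, the same sessions fall 2 to 8 h after the dose.

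**Would the compliance check catch it?** SAP 5.4 divides by days from first to last intake, so doses missed at the end leave the denominator too. Take a 14-day period, two capsules of each drug per day, and the last three days missed:
- On the SAP's denominator: 22/(11 × 2) = 100%.
- On the full period: 22/(14 × 2) = 78.6%.
- For subjects above 65, who start with one capsule for three days: (3 + 16)/(3 + 16) = 100%, against 19/25 = 76%.

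The below-80% criterion (PD#25) is therefore not met. With one or two doses missed, even the full-period figure passes (26/28 = 92.9% and 24/28 = 85.7%).

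**Possible dilution (illustration only).** Let f be the share of active-period tests taken late and r the share of modafinil left, and assume that the effect is proportional to drug level. The expected active-placebo difference is then multiplied by 1 - f(1 - r). The documents do not give f, so a range is shown.

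| Assumed f | Loss if all are at 24 h (r = 0.330) | Loss if all are at 72 h (r = 0.036) |
|---|---|---|
| 2% | 1.3% | 1.9% |
| 5% | 3.4% | 4.8% |
| 10% | 6.7% | 9.6% |
| 20% | 13.4% | 19.3% |

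**Power.** The stated 82% (paired t-test, 54 subjects, effect size 0.40, two-sided 0.05) reproduces as 82.3%. It belongs to the ESS. Neither document gives an effect size or power for PVT or MoCA.

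**The case against.** The limit is a tolerance for deviations from a plan that already calls for a visit-day dose, and nothing in the documents shows that even one period is affected. Treatment and washout duration, adverse events and logged deviations (PD#27, #30, #31) are reviewed case by case, and the blind data review report is not among the documents, so single periods may have been removed there. This stands as a limit on what can be claimed. It does not supply a written rule: SAP 5.1.2 refers the reader to 5.6 for how the review's decisions apply to efficacy.

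The effect also need not track plasma level hour by hour, and the SAP treats a washout as evaluable only from 6 days after the last intake. The shift towards zero is therefore an expectation, not a demonstrated result.

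The consequence is limited. The primary objective is safety, the main efficacy analysis is on the FAS, the trial is exploratory, and a pull towards no difference would not be expected to produce a false claim of benefit. All of this stands.

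Finally, a stricter rule has its own selection risk. It would tend to remove early discontinuation visits, where treatment may have stopped because of adverse events, and these may be unequally spread over treatments. This also stands and shapes the fix.

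**Conclusion.** The point holds as a mismatch between one evaluability rule and two same-day measures. Under the written rules, PVT and MoCA results from 24 to 72 h after the last dose count as on treatment in the Per Protocol analysis. The residual levels assume first-order decline at 15 h and 13 h; the shorter documented half-lives leave less. The expected direction is towards no active-placebo difference, provided that the effect falls as the drug is eliminated. The size is unknown.

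A reader might infer three stronger things that the documents do not support:
- That off-drug tests do enter the analysis and dilute it. The rule permits this; no count is given.
- That every late test has only 2% to 4% of drug left. That is the 72 h extreme; a single missed morning leaves about a third of modafinil and over a quarter of flecainide.
- That power falls from 82% to some lower figure. That would borrow the ESS effect size for endpoints with no stated power, in a supportive analysis for which none is claimed.

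**What to change.** For PVT and MoCA only, base the Per Protocol analysis on periods with IMP intake on the visit day before the first PVT or MoCA test. Alternatively, add a Per Protocol sensitivity analysis restricted to those periods. Keep the 3-day rule for the ESS and leave the FAS unchanged.

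Use diary intake times and actual test times. SAP 5.6.5 says that PVT times are in the eCRF. Neither document says that a MoCA time is recorded; if it is not, the first PVT time is the nearest anchor. Do not reuse the PK criterion: it refers to a sample drawn on arrival, so a subject who doses after that sample but before the 10:00 PVT would be dropped although tested on drug.

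Add one table of periods by treatment and days since last intake. It would show whether the issue matters at all.

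The cost is a sentence or two in the SAP, one derived flag and one table, apart from the MoCA time from data already collected. The rule can be set before unblinding. The downside is that some periods, including early discontinuation visits, leave a supportive analysis, possibly unequally by treatment, so exclusions should be reported by treatment.

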### 5.6.1 Key Efficacy Analysis

On visits VS1, VR, V1B, V1C, V2B, V2C, and V3B/EDV subjects will fill out the Epworth Sleepiness Scale (ESS) questionnaire. The ESS consists of 8 questions with the answers on the scale of 0-3. The ESS score is the sum of the 8 items and has a range of 0-24. The **key efficacy variable** in this trial is the change from baseline of the ESS score at the end of each treatment period (visits V1B, V2B, and V3B/EDV).

The ESS score change from baseline will be analysed using a mixed linear regression model with the fixed effects of treatment, period, treatment by period interaction, sequence, and baseline score, and subject nested within sequence as a random effect. The model will be estimated using the restricted maximum likelihood method (REML). Degrees of freedom for the fixed effects will be estimated using the Kenward-Roger approximation.

The following SAS code will be used in mixed linear regression modelling:

```
PROC MIXED DATA=<Dataset> METHOD=REML;  
  CLASS <Subject> <Treatment> <Period> <Sequence>;  
  MODEL <Change from Baseline> = <Treatment> | <Period>  
      <Sequence> <Baseline>  
      / DDFM = KENROG;  
  RANDOM int / SUBJECT=<Subject>(<Sequence>);  
  LSMEANS <Treatment> / PDIFF CL;  
RUN;
```

A statistically significant (p-value < 0.05) treatment by period interaction may indicate the presence of residual treatment (carryover) effects, which may bias the estimates of treatment effects. For this reason, if a statistically significant treatment by period interaction is found in the analysis of the key efficacy endpoint, the key efficacy analyses will be performed using data from the first period only. In such an event, the key efficacy endpoint will be modelled using an analysis of covariance (ANCOVA) model with the fixed effect of treatment and baseline score as a covariate.

The following SAS code will be used in the analysis of first-period data:

```
PROC MIXED DATA=<Dataset> METHOD=REML;  
  CLASS <Treatment>;  
  MODEL <Change from Baseline> = <Treatment> <Baseline>  
      / DDFM = KENROG;  
  LSMEANS <Treatment> / PDIFF CL;  
RUN;
```

Additional exploratory analysis of the carryover effect is defined in section 5.6.2.

The following tables, listings and figures will be provided:

[Table 15.3.1.1.1.S Summary of Epworth Sleepiness Scale Score – Full Analysis](#)

[Table 15.3.1.1.2.S Summary of Epworth Sleepiness Scale Score – Per Protocol](#)

[Table 15.3.1.2.1.T Summary of Epworth Sleepiness Scale Score – Full Analysis](#)

[Table 15.3.1.2.2.T Summary of Epworth Sleepiness Scale Score – Per Protocol](#)

The Epworth sleepiness scale score will be summarised using default summary statistics at each visit. The ESS change from baseline will be summarised at each post-baseline visit.

[Table 15.3.2.1.1 Analysis of Epworth Sleepiness Scale Score – Full Analysis](#)

[Table 15.3.2.1.2 Analysis of Epworth Sleepiness Scale Score – Per Protocol](#)

[Table 15.3.2.2.1 Analysis of Epworth Sleepiness Scale Score \(First Period\) – Full Analysis](#)

[Table 15.3.2.2.2 Analysis of Epworth Sleepiness Scale Score \(First Period\) – Per Protocol](#)

Estimates of each modelled effect will be displayed with standard errors, t-values and p-values. Contrast estimates will be displayed for the difference between each pair of treatments.

[Figure 15.3.1.1.S Subject-Level ESS Score Change from Baseline – Full Analysis](#)

[Figure 15.3.1.2.S Subject-Level ESS Score Change from Baseline – Per Protocol](#)

ESS score change from baseline at the end of every treatment period will be displayed for each subject stratified by treatment sequence.

[Figure 15.3.2.1.T Mean ESS Score Change from Baseline by Period – Full Analysis](#)

[Figure 15.3.2.2.T Mean ESS Score Change from Baseline by Period – Per Protocol](#)

The mean and standard deviation of ESS score change from baseline pooled by treatment at the end of every treatment period will be displayed using a scatter plot with error bars.

[Listing 16.2.9.1 Epworth Sleepiness Scale – Enrolled](#)

Epworth sleepiness scale results will be listed for each subject in the enrolled analysis set.

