Continuous efficacy endpoints – the change from baseline at each key visit (end of treatment period I, II, and III) in ESS, PVT and MoCA - will be analysed using a mixed linear regression model. The model will include the treatment, period, treatment by period interaction, sequence, and baseline scores as fixed effects, and the subject nested within sequence as a random effect.

Categorical efficacy endpoints – absence of residual somnolence and ESS responder status at each key visit – will be analysed using a mixed effects logistic regression model, with the treatment, period, treatment by period interaction, sequence, and baseline scores as fixed effects, and the subject nested within sequence as a random effect.

Treatment least square means and mean differences will be reported with their standard errors and 95% confidence intervals. The significance of the differences between Treatment A (THN102 Placebo), Treatment B (THN102 200/2) and Treatment C (THN102 200/18) will be assessed with a contrast t-test at the two-sided 5% level.

Supportive analysis

The same analysis will be repeated on the PP set, to assess robustness of the analysis of the variables from ESS and PVT and possibly on other efficacy results. Subgroup analyses may be performed to investigate the effect of the main demographics (age, gender) and disease characteristics (in terms of daily sleepiness extent, and cognitive impairment) on the efficacy outcomes.

The presence of a significant treatment by period interaction term in the main model may indicate a residual treatment (carryover) effect. In case of a significant treatment by period interaction, period I results will be analysed separately, and further analyses will be performed to explore the carry-over effects. The methods for evaluation of carryover effects will be defined in the SAP.

Safety analysis

Safety data will be summarised using summary statistics and frequency tabulations, as appropriate.

Pharmacokinetics

- Plasma concentrations of modafinil and flecainide at visits VR, V1B, V1C, V2B, V2C and V3B, considering time after last IMP intake.
- Concentration-time data per treatment and subject for modafinil and for flecainide. Plasma concentrations and time post IMP intake, to assess range of exposure at steady state for each treatment.

Trial flow chart

	VS1	VS2	VR	V1A	V1B	V1C	V2A	V2B	V2C	V3A	V3B/ EDV ¹¹	V3C

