8.3.1. Efficacy

Continuous efficacy endpoints – the change from baseline at each key visit (end of treatment period I, II, and III) in ESS, PVT and MoCA - will be analysed using a mixed linear regression model. The model will include the treatment, period, treatment by period interaction, sequence, and baseline scores as fixed effects, and the subject nested within sequence as a random effect.

Categorical efficacy endpoints – absence of residual somnolence and ESS responder status at each key visit – will be analysed using a mixed effects logistic regression model, with the treatment, period, treatment by period interaction, sequence, and baseline scores as fixed effects, and the subject nested within sequence as a random effect.

Treatment least square means and mean differences will be reported with their standard errors and 95% confidence intervals. The significance of the differences between Treatment A (THN102 Placebo), Treatment B (THN102 200/2) and Treatment C (THN102 200/18) will be assessed with a contrast t-test at the two-sided 5% level.

Handling of missing values/censoring/discontinuations: Subjects who misused their planned treatments or doses or have missing outcome measurements will not be excluded from the primary analysis in the FAS. Under the assumption that outcomes are missing at random, the mixed-model can propagate uncertainty due to missing data into estimates of treatment efficacy and other quantities of interest. Hence, missing data will not be imputed or replaced prior to the analysis.

Supportive analysis: The same analysis will be repeated on the PP set, to assess robustness of the analysis of the variables from ESS and PVT and possibly on other efficacy results. Subgroup analyses may be performed to investigate the effect of the main demographics (age, gender) and disease characteristics (in term of daily sleepiness extent, and cognitive impairment) on the efficacy outcomes.

The presence of a significant treatment by period interaction term in the main model may indicate a residual treatment (carryover) effect. In case of a significant treatment by period interaction, period I results will be analysed separately, and further analyses will be performed to explore the carry-over effects. The methods for evaluation of carryover effects will be defined in the SAP.

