## 2.6 Sample Size

For sample size planning ESS was considered to be the key efficacy endpoint. Solid information on the expected difference between placebo and THN102 dose and the associated intrasubject variance were not available. Using results reported in Adler et al. [4] as a rough orientation an effect size of 0.40 may constitute a conservative estimation for the comparison of the high THN102 dose with placebo. A sample size of 54 subjects will have a power of 82% to detect this effect size based on a paired t-test with a 0.05 two-sided significance level. To account for drop outs 60 subjects will be randomised.

In this exploratory phase 2a study, no adjustment for multiple testing will be applied.

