### 5.6.2 Key Efficacy Endpoint Carryover Effect Estimation

If the key efficacy endpoint analysis shows a statistically significant treatment by period interaction ( $p$ -value  $< 0.05$ ), modified key efficacy analyses will be performed to adjust for potential first-order carryover effects on the ESS score. For these analyses, the treatment of the previous treatment period will be assigned to each observation. The treatment by period interaction in the original efficacy model will not be included.

The treatment effects at end-of-treatment visits V1B, V2B and V3B will be estimated using a mixed linear regression model with the fixed effects of treatment, period, sequence, and residual treatment, baseline score as a covariate, and the random effect of subject nested within sequence. The carryover effect estimation will be performed using the following SAS code:

```
PROC MIXED DATA=<Dataset> METHOD=REML;
  CLASS <Subject> <Treatment> <Period> <Sequence> <LagTreatment>;
  MODEL <Change from Baseline> = <Treatment> <Period> <Sequence>
    <Baseline> <LagTreatment>
    / DDFM = KENROG;
  RANDOM int / SUBJECT=<Subject>(<Sequence>);
  LSMEANS <Treatment> / PDIFF CL;
RUN;
```

The following tables will be presented:

Table 15.3.2.3.1 Analysis of Epworth Sleepiness Scale Score Adjusted for Carryover – Full Analysis

Table 15.3.2.3.2 Analysis of Epworth Sleepiness Scale Score Adjusted for Carryover – Per Protocol

Estimates of each modelled effect will be displayed with standard errors, t-values and p-values. Contrast estimates will be displayed for the difference between each pair of direct treatment effects.

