#### **5.6.5 Psychomotor Vigilance Test (PVT)**

On visits VR, V1B, V1C, V2B, V2C, and V3B/EDV subjects will undergo 3-minute Psychomotor Vigilance Task evaluations. PVT will be performed up to four times during each visit: at 10:00 h, 12:00 h, 14:00 h, and 16:00 h ( $\pm 15$  minutes each) by default. If the default PVT schedule is too burdensome for a particular subject, it may be individually adapted to at least 3 assessments with a time window of at least 1 hour between each PVT assessment. The actual time of each PVT assessment will be collected in the eCRF.

The following PVT variables will be collected at every visit and timepoint:

- Mean response time (ms)
- Number of lapses
- Number of total errors

A failure to react or any reaction exceeding 500 ms is considered a lapse. A reaction without stimulus or under 100 ms is considered a false start. Lapses and false starts are counted towards total errors.

For each PVT variable, the mean value during a visit will be used for analysis.

The PVT mean response time will be analysed using a mixed linear regression model as described in Section 5.6.1.

In the case that a statistically significant ( $p$ -value  $< 0.05$ ) treatment by period interaction is found in the analysis of the PVT mean response time, an additional analysis will be performed using only data collected during the first treatment period. The statistical model will be adjusted as described in Section 5.6.1.

The following tables, listing, and figures will be presented:

Table 15.3.7.1.1.S Summary of PVT Mean Response Time – Full Analysis

Table 15.3.7.1.2.S Summary of PVT Mean Response Time – Per Protocol

Table 15.3.7.2.1.T Summary of PVT Mean Response Time – Full Analysis

Table 15.3.7.2.2.T Summary of PVT Mean Response Time – Per Protocol

PVT mean response time will be summarised using default summary statistics at each visit. The change from baseline will be summarised at each post-baseline visit.

Table 15.3.8.1.1.S Summary of PVT Errors – Full Analysis

Table 15.3.8.1.2.S Summary of PVT Errors – Per Protocol

Table 15.3.8.2.1.T Summary of PVT Errors – Full Analysis

Table 15.3.8.2.2.T Summary of PVT Errors – Per Protocol

The number of lapses and number of total errors during PVT evaluation will be summarised using default summary statistics at each visit. The change from baseline will be summarised at each post-baseline visit.

Table 15.3.9.1.1 Analysis of PVT Mean Response Time – Full Analysis

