## **7. CHANGES TO THE ANALYSIS AS LAID DOWN IN THE PROTOCOL AND AMENDMENTS**

The definition of the Per Protocol set was changed to include subjects with major protocol deviations, if they have at least one treatment period unaffected by a major protocol deviation. Per Protocol analysis will be performed on all trial periods unaffected by a major protocol deviation.

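### A significant treatment-by-period test makes a first-period ANCOVA the key ESS analysis, with power of about 24-33% instead of the planned 82%

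*SAP*

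**What the plan says.** SAP 5.6.1 fits a three-period mixed model to ESS change from baseline, with treatment, period, their interaction, sequence and baseline. If the interaction has p<0.05, "the key efficacy analyses will be performed using data from the first period only", using an ANCOVA on treatment and baseline.

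Protocol 8.3.1 has the same trigger but a milder consequence, under its supportive analyses: "In case of a significant treatment by period interaction, period I results will be analysed separately". The synopsis agrees: "period I results will be analysed separately, and further analyses will be performed to explore the carry-over effects". Both leave the carryover methods to the SAP.

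For PVT, SAP 5.6.5 says that after a significant interaction "an additional analysis will be performed using only data collected during the first treatment period". Sections 5.6.3 (responder rate), 5.6.4 (residual somnolence), 5.6.6 (MoCA) and 5.6.7 (actigraphy) do the same.

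The three-period ESS result stays in the output list ("Table 15.3.2.1.1 Analysis of Epworth Sleepiness Scale Score – Full Analysis"). SAP 5.6.2 adds a carryover-adjusted three-period model, run only after the same trigger, in which "the treatment of the previous treatment period will be assigned to each observation". SAP section 7, on changes from the protocol, has one entry: "The definition of the Per Protocol set was changed to include subjects with major protocol deviations".

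**The concern.** ESS is the endpoint on which the trial was sized, and the sizing is for a within-subject comparison (SAP 2.6). It is also the only endpoint whose key analysis is replaced, not supplemented, after the interaction test. The replacement compares three parallel groups and uses one third of the data. Neither document gives its power.

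The rule would be reasonable if the trigger identified carryover well and the first-period estimate were then the more accurate one. If neither is true, a chance finding in about 1 trial in 20 moves the key label from the powered result to a weak one, and a dispute over which ESS result counts would arise after unblinding.

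**Working it through.** **Inputs.** From SAP 2.6: 54 evaluable subjects (60 randomised), effect size 0.40 for the high dose (C) against placebo (A), two-sided 5%. From the design: six equal sequences, so each treatment comes first in two of six, giving 18 per arm in period I (20 if 60 subjects). The documents give no intrasubject variance or correlation. I assume equal correlation ρ among baseline and the three periods, with main range 0.5-0.7. The SD of paired differences is set to 1, and the low-dose effect is equal to, or half of, the high-dose effect.

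**1. The plan's own figure.** "A sample size of 54 subjects will have a power of 82% to detect this effect size based on a paired t-test": noncentrality 0.40 × √54 = 2.94 with 53 df gives 82.3%. Reproduced. The three-period model has SE 1/√54 = 0.136 and 2 × 54 − 8 = 100 within-subject df, so power is about 83%.

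**2. First-period ANCOVA.** The SD of one measurement is 1/√(2(1−ρ)), and baseline adjustment multiplies it by √(1−ρ²). With m per arm the SE is √(2/m) × √((1+ρ)/2), with 3m − 4 df.

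| m per arm | ρ | SE | 0.40/SE | Power |
|---|---|---|---|---|
| 18 | 0.5 | 0.289 | 1.39 | 27% |
| 18 | 0.7 | 0.307 | 1.30 | 25% |
| 20 | 0.5 | 0.274 | 1.46 | 30% |
| 20 | 0.7 | 0.292 | 1.37 | 27% |

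Over ρ from 0 to 0.8 and both sample sizes, power runs from about 42% down to 24%. If baseline predicted nothing it would be 15-24%.

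**3. How often the trigger fires** (simulation, 54 subjects, interaction F with 4 and 100 df). The rate is 5% without carryover. With carryover at 25%, 50% and 100% of the effect it is 5-5.5%, about 6-7% and 9-11%. Even at 100%, roughly 90% of affected trials are not flagged.

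**4. When it fires without carryover.**
- First-period power is 28-33%; the three-period contrast in the same trials keeps 82-86%.
- In 55-60% of these trials the three-period C−A result is significant and the first-period result is not. The reverse occurs in about 2%.
- With no treatment effect, the first-period test rejects in about 8-10% of triggered trials, because its estimate is correlated with the interaction.

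**5. Averaged over all trials without carryover.** Power is about 0.95 × 0.83 + 0.05 × 0.30 = 0.80, against 0.83 without the switch. With 60 subjects it is 84% against 87%. Overall type I error stays at 4.9-5.5%.

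**6. Accuracy under carryover.** Each ordered pair of treatments occurs in two of the six sequences, so the unadjusted C−A estimate is biased by minus one third of C's carryover. At 100% that is 0.40/3 = 0.133, and the RMSE is √(0.136² + 0.133²) = 0.19.

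| Carryover (% of effect) | 0 | 25 | 50 | 100 |
|---|---|---|---|---|
| Three-period RMSE | 0.14 | 0.14 | 0.15 | 0.19 |
| First-period RMSE | 0.29-0.31 | 0.29-0.31 | 0.29-0.31 | 0.29-0.31 |
| Carryover-adjusted RMSE (SAP 5.6.2) | 0.15 | 0.15 | 0.15 | 0.15 |

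Within triggered trials the figures are 0.33-0.37 for the first period and 0.13-0.19 for the three-period model.

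**7. The SAP 5.6.2 model.** Its SE is 0.152, which is 12% above 0.136. 0.40/0.152 = 2.63, so power is 74%. SAP 5.6.2 does not say what the lag variable is in period I, where there is no previous treatment. Coding it as placebo, or as zero in numeric contrasts, works. A separate *none* level keeps the treatment differences but makes the treatment LS-means non-estimable. Left missing, PROC MIXED would drop the 54 period-I rows, leaving 108 of 162; the SE becomes 0.222 (1.63 times 0.136) and power about 43%.

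**The case against.** The strongest counter-argument is that little depends on the word *key*. Safety is the primary objective, the trial is exploratory with no multiplicity adjustment, no success rule is tied to ESS, and all three ESS tables would exist after a trigger. The average loss is about 3 points of power. This stands, and it limits how serious the point is.

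A second argument is that a sponsor may prefer an estimate free of carryover bias to one with smaller total error. Interval coverage gives this some support. In triggered trials (low-dose effect equal to high-dose, correlation 0.5), coverage for three-period against first-period is 93% against 91% without carryover, 89% against 91% at 50%, and 84% against 93% at 100%. But the carryover-adjusted model deals with the bias at far lower cost in precision, so this argues for that model and not for discarding two thirds of the data.

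Third, SAP 5.6.2 describes its models as modified key analyses, so the label may not move to period I alone. SAP 5.6.1, however, calls the same work additional and exploratory. The labels conflict and need settling.

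Fourth, half-lives of about 13-15 h (protocol Table 1) against a one-week washout make large pharmacokinetic carryover unlikely, and end-of-washout ESS offers another check. Both are true, but they weaken the case for the switch: if carryover is unlikely, a significant interaction is probably chance.

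Finally, SAP 5.6.2 intends to use the V1B data, so a missing lag would be a programming slip and not the plan. I agree; that part is a clarification.

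**Conclusion.** The concern holds. The switch in SAP 5.6.1 rests on a test that hardly distinguishes carryover from chance. It replaces the key ESS analysis with one of about 25-30% power (28-33% given the trigger at 54 subjects), and the replacement has the larger total error at every carryover level examined, including in triggered trials. It gives period I a status that protocol 8.3.1 does not, differs from the SAP's handling of the other endpoints, and is not listed in SAP section 7.

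The damage is concentrated in the roughly 5% of trials without carryover in which the test fires. The power figures depend on the assumed correlation, but the ordering of the analyses holds over the whole range from 0 to 0.8. Given the secondary, exploratory status of ESS, this should be changed but does not threaten the trial.

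**What to change.** - **SAP 5.6.1:** keep the three-period mixed model as the key ESS analysis whatever the interaction p-value. Report the first-period ANCOVA as an additional, supportive analysis. This matches protocol 8.3.1 and the other endpoints, which need no change.
- **SAP 5.6.2:** run the carryover-adjusted model as a sensitivity analysis regardless of the interaction test. State the period-I lag value, for example two numeric contrasts (previous B, previous C) set to 0 in period I. Use one label for this model in both sections.
- **SAP section 7:** if the sponsor keeps the switch, list it as a change from the protocol.

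The cost is SAP wording, a few lines of SAS, and Tables 15.3.2.3.1 and 15.3.2.3.2 produced always instead of conditionally. No new data are needed.
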